Objectives

The objectives of this data collection activity are to:

- a) Describe the baseline demographics, clinical and laboratory profile of patients who ever received DRV and/or ETR, at the time of initiation on DRV and/or ETR,
- b) Describe the clinical and laboratory profile of patients who ever received DRV and/or ETR every 6 months from the first data collection point through 2021,
- c) Describe dynamics in HIV drug resistance mutations among patients who fail treatment on new regimens, including DRV and/or ETR.
- d) Describe demographics, clinical and laboratory profile of young adults who transition out of the donation program after the age of 25 years at 12 months after their transition.

Use of Results of this Evaluation

The de-identified data from each participating country will be analyzed and reported to relevant MOH. These overall demographic and clinical findings will be used to describe the children and adolescents who have received DRV and/or ETR up through each time point of data collection. Data from this evaluation will be used as resource when countries review their national guidelines for second- and third-line ART.

The findings will be presented at regional and international scientific meetings or conferences.

Data summarized across New Horizons countries will be shared with programmatic stakeholders and potential New Horizons partners. These stakeholders include the Centers for Disease Control and Prevention (CDC), the United States Agency for International Development (USAID), the United States Office of the Global AIDS Coordinator (OGAC), IAS CIPHER, the Clinton Health Access Initiative (CHAI), PFSCM, various industry partners such as Janssen and Merck, and others.

III. Procedures and Methods

Targeted Facilities

Data collection will occur in the existing clinical programs that are currently managing patients on ART regimens, which include at least one product (i.e., DRV and/or ETR).

Sources of Data

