Data will be abstracted from individual patient files/cards stored at the health facility. Only those patient files which represent recipients of DRV and/or ETR will be accessed for the purposes of this activity. All data collection tools and processes will be approved by the in-country IRB. Each patient will be assigned a unique Study identification (ID) number and data collection forms will be linked to the patient using this unique identifier only. The data abstraction team will maintain a master document (“link log”) that allows linking of files of participants to the unique ID. Access to this document will be limited to members of the abstracting team and the evaluation team.

Methods and Timeline

The current data collection activity is intended to describe the demographic, clinical and laboratory characteristics of patients at the point of initiation on DRV and/or ETR and b) the most recently recorded data at the time of most recent data collection point (every six months). Patients will be stratified by the duration of time on ETR and/or DRV.

Members of the abstraction team will visit each participating facility which is handling patients who ever used DRV and/or ETR on a convenient and mutually agreeable day. Because the volumes of patients on DRV and/or ETR are anticipated to be low, data collection activities at each facility are not anticipated to take more than a few hours on a single day. Data abstraction from each patient is expected to be repeated approximately every six months from the last data collection point. The last data collection activity is anticipated to occur in December 2021.

Key Variables

Table 1: Key variables and data source.

Objectives	Variables	Data sources	Comment
a) Describe the demographics, clinical and laboratory profiles of patients who ever received DRV and/or ETR, at the time of initiation on DRV and/or ETR.	
- Age- Gender- Weight- Height (when available)	
- Clinical card- ART register- Lab register	Data collection team should use ART and Lab registers, among others, to complement data not found in the clinical cards

	
 - Viral load at the time of DRV and/or ETR initiation - Baseline ARV drug resistance mutations 		

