b) Describe clinical and laboratory profile of patients who ever received DRV and/or ETR every 6 months from the first data collection point through 2021.	
 - Weight - Height - Most recent viral load - Any new genotypic resistance assay results 	
 - Clinical records - ART registers - Lab registers 	Data collection team should abstract data from ART clinical file and ART and lab registers, among other registers. These data will be disaggregated by time duration from last visit as 6, 12, 18, 24, 30 and 36 months.
c) Describe dynamics in HIV drug resistance mutations among patients who fail treatment on new regimens, including DRV and/or ETR.	
 - Weight - Height - Viral load - Duration receiving DRV/ETR - Genotypic resistance test results - Lab based suggested regimen by clinical virologist 	
 - Clinical records - Lab registers 	These data will be abstracted from Laboratory form/register, among other registers.
d) Describe demographics, clinical and laboratory profile of young adults who transition out of the donation program after the age of 25 years at 12 months after their transition.	
 - Weight - Height - Most recent viral load - Any new genotypic resistance assay results 	
 - Clinical records - ART registers - Lab registers 	Data collection team should abstract data from ART clinical file and ART and lab registers, among other registers.

Table 2. Schedule of Evaluation data extraction from each clinical file

Study Activity	Baseline	6 months	12 months	18 months	24 months	30 months	36 months
Demographics	X						
Review Patient Clinical file	X	X	X	X	X	X	X
Record of co-morbidities, such as TB, etc.	X	X	X	X	X	X	X
Weight	X	X	X	X	X	X	X

Height (if available)	X	X	X	X	X	X	X
Results of Viral Load	X ¹	X	X	X	X	X	X
Recorded Clinical diagnosis of Treatment Failure	X	X	X	X	X	X	X
Genotypic Resistance mutation	X	X	X	X	X	X	X
Records of pregnancy	X	X	X	X	X	X	X

Data Handling and Analysis

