EGPAF will fund the data collection, data entry, analyses and reporting activities. Data will be abstracted from patient files, ART register or laboratory registers at participating facilities by an EGPAF staff member specifically trained in the objectives and methods of the current assessment (the “abstraction team”). All evaluation team members will be trained in patient confidentiality and human subject protection. Data abstraction will occur in a private location of the health facility to minimize any risk of unauthorized viewing of medical records.

Routinely collected patient-level data will be abstracted from patient files and recorded into a password protected database. Each patient will be assigned a unique study ID and data collection will be linked to the patient using this unique ID only. A master document, “link log” that permits linking of the patient’s name to the unique identification number will be maintained in password protected files by the abstracting team, with access to this document limited to members of the abstracting team and the evaluation team only. Baseline demographic, clinical and laboratory data will be summarized using frequencies and percentages for categorical variables and mean (SD) or median (IQR) for continuous variables depending on their distributions.

Clinical and laboratory follow-up data will be summarized using appropriate descriptive statistics stratified by duration on DRV/ETR. In addition, patient records will be stratified by duration of time on DRV/ETR, and retention on DRV/ETR regimen will be described.

Other analyses may also be conducted using the de-identified data.

Ethical Considerations

Institutional Review Board and Informed Consent

This protocol will be reviewed by an Institutional Review Board (IRB) in the US and an ethical review committee in each of the project countries. The local in-country ethics committees will also receive and approve country-specific details about the evaluation.

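### The only time axis given for objective (c) is time on DRV/ETR, which pools never-suppressed and recently rebounded patients; suppression history and viraemic time should be reported beside it

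*Combined protocol and SAP*

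**What the plan says.** The Objectives section states aim (c) as: "Describe dynamics in HIV drug resistance mutations among patients who fail treatment on new regimens, including DRV and/or ETR". In Table 1 (Key Variables), the row for this objective lists weight, height, a laboratory-suggested regimen and "Viral load - Duration receiving DRV/ETR - Genotypic resistance test results". Duration on the drugs is the only time variable in that row. The row asks for no date of viral load, date of genotype sample or date of failure.

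The stratifier appears in two other places. Methods and Timeline says: "Patients will be stratified by the duration of time on ETR and/or DRV". Data Handling and Analysis says: "Clinical and laboratory follow-up data will be summarized using appropriate descriptive statistics stratified by duration on DRV/ETR". Genotypes are laboratory follow-up data, so the second sentence covers them.

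Table 2 schedules "Results of Viral Load", "Recorded Clinical diagnosis of Treatment Failure" and genotypic resistance at baseline and at 6, 12, 18, 24, 30 and 36 months. No planned analysis uses these rows to date the onset of failure, to separate patients who never suppressed from those who rebounded, or to derive time with unsuppressed virus. Neither failure nor an unsuppressed viral load is defined.

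**The concern.** Dynamics means change over time, so the choice of clock decides what the result for objective (c) describes. New mutations are selected while virus replicates under drug. Among failing patients, time on DRV/ETR adds suppressed time, when little selection is expected, to viraemic time, when it is. A patient viraemic for all 24 months and a patient suppressed for 20 months who then rebounded both count as 24 months.

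The mutation percentage in a duration stratum then depends on two things: how fast resistance develops during viraemia, and what share of the stratum never suppressed. The planned stratification cannot separate them. A rise, a plateau or a fall across duration strata could come from case mix alone. Under Use of Results of this Evaluation, the findings are meant to inform countries' reviews of second- and third-line guidance, so it matters what the percentages can be taken to mean.

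**Working it through.** The plan is descriptive and has no sample size, rate or event figure to reproduce. The check sets the text against a simple illustration.

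**Inputs from the documents.** Stratifier: duration on DRV/ETR (Data Handling and Analysis). Six-monthly points to 36 months (Table 2). Previous baseline evaluation: 48 patients at nine sites (Introduction, Programmatic Response).

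**Assumed inputs (none is in the documents).** A constant rate r of first new mutations per viraemic month, the time since rebound, and the share w of the stratum that never suppressed.

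**1. Two patients in one 24-month stratum.** P(at least one new mutation) = 1 − exp(−r × viraemic months). The stratum percentage is w × P(never suppressed) + (1 − w) × P(rebound). Rebound is set at 4 months before the genotype.

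| r per month | Never suppressed (24 months) | Rebound (4 months) | w = 20% | w = 50% | w = 80% |
|---|---|---|---|---|---|
| 0.02 | 1 − exp(−0.48) = 38% | 1 − exp(−0.08) = 8% | 14% | 23% | 32% |
| 0.05 | 1 − exp(−1.2) = 70% | 1 − exp(−0.2) = 18% | 28% | 44% | 60% |
| 0.10 | 1 − exp(−2.4) = 91% | 1 − exp(−0.4) = 33% | 45% | 62% | 79% |

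For example, at r = 0.05 and w = 20%: 0.2 × 0.699 + 0.8 × 0.181 = 0.285. Within each row the rate is the same for every patient; only the mix differs.

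**2. A different set of assumptions.** With 0.5 per viraemic year and rebound 6 months ago, the two groups are at 1 − exp(−1.0) = 63% and 1 − exp(−0.25) = 22%. The 24-month stratum reads 30%, 43% or 55% at w = 20%, 50% or 80%.

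**3. Effect on an apparent trend.** Same assumptions as step 2, strata at 12, 24 and 36 months:
- w fixed at 50%: 31%, 43%, 50%.
- w falling 80%, 50%, 20%: 36%, 43%, 33%.

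The rate is identical in both lines, yet one rises steadily and the other rises and then falls.

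**4. Which viraemic clock.** Take a patient unsuppressed at 6 months, suppressed at 12 and 18, unsuppressed at 24, with a genotype at 24.
- Counting from the first unsuppressed value on drug gives 24 − 6 = 18 months, although the patient was suppressed at both measurements in between.
- Counting from the current episode places onset between 18 and 24 months, so 0 to 6 months of viraemia.
- For a patient who never suppressed, counting from the first on-drug viral load starts late; the clock should start at DRV/ETR initiation.

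**5. Likely numbers.** The size of the present cohort is not stated. If it resembled the 48 patients described before and 20% to 40% failed (assumed), that is 9.6 to 19.2 failing patients. Over six six-monthly bands this is about 2 to 3 per band, before any split by class. Ten countries are now listed, so the true figure may be larger.

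**The case against.** The strongest reply is that no table for objective (c) is specified. Table 1 lists duration as a variable to collect, and the stratification is one general sentence for all follow-up data. Baseline and later genotypes would also allow a within-patient comparison. That is fair: this is partly under-specification. But the plan commits to none of the alternatives, and the one stratifier it does state is time on drug.

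A second reply is that viral load and the recorded failure diagnosis are already in Table 2, and that "Other analyses may also be conducted using the de-identified data". The gap is indeed mainly one of analysis definition. It is not closed, because row (c) asks for no dates, and Methods and Timeline takes the latest recorded value at each round, which can miss the start of a rebound.

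Third, a viraemic clock has limits. Follow-up abstraction runs from the first data collection point, while the donation programme dates from 2014, so a patient who started earlier may have no abstracted viral load for a long stretch. A reader might infer that onset is always known to within one six-month round; the documents do not support that. Adherence appears in neither table, so viraemic strata would still mix patients taking and not taking the drugs. These points stand and shape the remedy.

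Fourth, patient volumes are expected to be low. This argues for reporting viraemic time beside duration on drug, since replacing duration would discard a listed descriptor for a measure that will sometimes be unknown.

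**Conclusion.** The point holds as a limit on interpretation. Stratified only by duration on DRV/ETR, the mutation percentages for objective (c) pool very different viraemic exposure and can move with the share of never-suppressed patients. Under the assumed rates of 0.02 to 0.10 per viraemic month, shifting that share from 20% to 80% moves the 24-month figure from 14% to 32% at the lowest rate and from 45% to 79% at the highest. The direction needs only that mutations accumulate with viraemic time on drug and that rebounders have had less of it. The size rests wholly on assumed rates, mixes and rebound times, and shows what could happen, not what is likely.

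A reader might go further and infer that ministries will take a difference between countries in case mix for a property of the drugs. The documents plan no between-country comparison of resistance; they describe reporting each country's data to its ministry and sharing cross-country summaries. That misreading is only a possibility. No error rate or sample size is affected, since nothing is tested.

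**What to change.** Keep duration on DRV/ETR as a descriptor, and make these additions for objective (c):

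1. In Table 1 row (c), add the dated viral loads since DRV/ETR initiation that are found in the files, and the genotype sample date.
2. State the viral-load threshold that the analysis uses for unsuppressed.
3. Classify each failing patient as never suppressed on DRV/ETR, rebound after suppression, or unknown where no on-drug viral load is on file. Use the viral loads together with the recorded failure diagnosis already in Table 2.
4. Report new mutations, relative to the baseline genotype, by this class. Alongside duration on drug, report them by time from the start of the current viraemic episode to the genotype date. For never-suppressed patients the start is DRV/ETR initiation. For rebounders it is the interval between the last suppressed and the next unsuppressed viral load.
5. Use a few broad time bands, or a patient-level listing if numbers are small.

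The cost is extra date abstraction from registers already being read, one classification rule and one table or listing. Onset remains interval-censored, possibly over more than one round for patients who started before the first abstraction. Adherence remains uncaptured, and cells become smaller. The report should say so.

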Janssen (the Pharmaceutical Companies of Johnson & Johnson), the Elizabeth Glaser Pediatric AIDS Foundation (EGPAF), the Partnership for Supply Chain Management (PFSCM), the Collaborative Initiative for Pediatric HIV Education and Research (CIPHER) of the International AIDS Society (IAS), Right to Care, and The Relevance Network have partnered to implement the *New Horizons Advancing Pediatric HIV Care Collaborative* (New Horizons Collaborative) to improve and scale-up pediatric HIV/AIDS care and treatment through increased awareness, research, health systems strengthening, and improved access to HIV/AIDS medicines.

There are various ways that Ministries of Health (MOH) can access DRV and/or ETR, such as through the Global Fund to Fight AIDS, Tuberculosis, and Malaria or other global donors, as well as direct purchase from the manufacturer. However, a primary source of DRV and ETR for pediatric populations in sub-Saharan Africa is through the New Horizons DRV/ETR *Donation Program*. Under the New Horizons Collaborative, a DRV/ETR Donation Program was launched in 2014 to increase access to pediatric HIV medicines for children experiencing ART failure. Under this program, Janssen provides DRV (PREZISTA®) and/or ETR (INTELENCE®) free of charge to eligible national HIV/AIDS programs in sub-Saharan Africa, for use in children and adolescents up to 25 years of age. Upon turning 25 years (or before as required by the national HIV/AIDS program), patients using donated products will be transitioned into the countries' HIV treatment programs for adults as designated by the national HIV program. Under this Donation Program, DRV in combination with ritonavir (RTV) may be used for either second- or third-line treatment after failure on lopinavir/ritonavir (LPV/r) and/or in individuals with virus that has multiple PI resistance mutations. Of note, the Donation Program does not endorse the use of DRV (along with RTV) as second- or third-line therapy for patients who have previously received only NNRTI-based ART regimens (e.g., 2 NRTIs plus nevirapine or efavirenz).

In order to be eligible for participation in the New Horizons Collaborative, countries must satisfy the following criteria:

1. Applicant country must be located in sub-Saharan Africa or else considered to be a Least Developed Country as defined by the United Nations
2. Medicine donation is legal in the applicant country

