EGPAF has been provided with funding by Johnson & Johnson Services to manage the country application process and convene the third-party review committee for country selection. EGPAF is also responsible for provision of technical assistance (TA) to national HIV/AIDS programs engaged in the New Horizons Collaborative. In 2014, EGPAF volunteered to conduct a collection of baseline demographic and clinical data for patients receiving DRV and/or ETR through in New Horizons Collaborative countries. The evaluation included 48 patients (45.8% female; median age=15 years) from nine clinical sites in Zambia, Swaziland, Kenya and Lesotho.^{vi} Most children (87.5%) had received ≥ 2 prior ART regimens; 81.2% had received lopinavir/ritonavir-based ART prior to switch. ARV drug resistance was common; of 47 patients with genotype results, 87.2% had ≥ 1 NRTI-resistance mutation (RM), predominantly M184V; 65.9% had ≥ 1 non-NRTI-RM, including 57.4% with ≥ 1 ETR-RM; 63.8% had ≥ 3 protease inhibitor RM, including 42.6% with ≥ 1 DRV-RM. For new ART regimens, DRV and RAL were most frequently prescribed (83.3%; n=40 on DRV and raltegravir, each). Eighteen patients (37.5%) were initiated on the NRTI-sparing ART.^{vi} These data reflect baseline information on children receiving DRV and/or ETR through New Horizons but did not capture new ART regimen treatment response. Hence, EGPAF is proposing to conduct a similar data collection from children and adolescents receiving DRV and/or ETR. For each patient, we will collect demographic, clinical and laboratory data (1) as recorded at the time of initiation on DRV and/or ETR, and (2) updated information approximately every six months, through 2021. New patients will be added to the dataset who have been enrolled since the previous data collection point.

Prior to the inception of the New Horizons Collaborative, no multi-country data were collected regarding the demographic or clinical characteristics of the target patient population (i.e., children, adolescents, and young people < 25 years in need of second- or third-line HIV/AIDS treatment). Therefore, the current activity proposes to collect cross-sectional demographic and clinical data at baseline and every six months for patients receiving DRV and/or ETR across participating New Horizons countries. This activity will comprise data abstraction of a key demographic, clinical, laboratory and case history indicators and outcomes on each patient who ever received DRV and/or ETR.

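### Follow-up results are grouped by an undefined duration on DRV/ETR that can itself depend on outcome, so trends across the groups cannot be read as response over time

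*Combined protocol and SAP*

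**What the plan says.** Section III, Methods and Timeline: "Patients will be stratified by the duration of time on ETR and/or DRV". Data Handling and Analysis repeats the rule for results: "Clinical and laboratory follow-up data will be summarized using appropriate descriptive statistics stratified by duration on DRV/ETR". The sentence after it adds that "retention on DRV/ETR regimen will be described". The values summarised are the latest ones on file at each six-monthly collection.

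Table 1, row b, gives another axis for the same follow-up data: "These data will be disaggregated by time duration from last visit as 6, 12, 18, 24, 30 and 36 months". Table 2 schedules extraction at baseline and at 6 to 36 months, while objective b counts six-month steps from the first data collection point.

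The Programmatic Response section sets the population, covering "outcomes on each patient who ever received DRV and/or ETR". It also describes rolling entry ("New patients will be added to the dataset who have been enrolled since the previous data collection point") and an age exit ("Upon turning 25 years (or before as required by the national HIV/AIDS program), patients using donated products will be transitioned").

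Nowhere does the plan say whether duration means time on drug or time since starting, what the denominator of each group is, or where patients who stopped, died or were lost are placed.

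**The concern.** On its ordinary meaning, duration on DRV/ETR is time spent on the drugs. That time can be cut short by failure followed by a regimen change, by death or by loss to care. Objective c expects some failures on the new regimens. Sorting viral loads by such a variable conditions on something that may depend on response. The make-up of the groups can then shift from short to long duration, and the shift can look like a change in response.

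A table running from short to long duration invites a reading as durability. Under Use of Results, the findings are to inform countries' reviews of second- and third-line guidance, so an artefact of patient selection could carry weight there.

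**Working it through.** The plan states no suppression, failure or stopping rate, so there is no figure of its own to reproduce. The check asks whether the stated grouping can create a trend when no patient changes. **All rates below are assumptions.**

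**Inputs.** A share p = 0.70 of starters is always suppressed and 0.30 never is. Per 6 months, a fraction h_r of suppressed and h_f of unsuppressed patients stops. There are six intervals to 36 months.

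**Model A, patients still on drug.** Share suppressed after k intervals = p(1−h_r)^k / [p(1−h_r)^k + (1−p)(1−h_f)^k].

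Per 100 starters with h_r = 0.03 and k = 6, suppressed and on drug = 70 × 0.97^6 = 58.3. Unsuppressed and on drug:
- h_f = 0.06: 30 × 0.94^6 = 20.7, so 58.3/79.0 = 73.8%
- h_f = 0.10: 30 × 0.90^6 = 15.9, so 58.3/74.3 = 78.5%
- h_f = 0.15: 30 × 0.85^6 = 11.3, so 58.3/69.6 = 83.7% (75% at 12 months and 80% at 24 months on the way)

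**Model B, all ever-treated patients grouped by achieved duration at one data cut.** Entry is even over 36 months and stoppers are placed in the group where they stopped. The weight of a class with stopping rate h in group j (1 to 6) is (1−h)^(j−1) × [1 + (6−j)h]/6.

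For h_r = 0.03 and h_f = 0.15:
- Group 1: 0.70 × 1.15 = 0.805 against 0.30 × 1.75 = 0.525, so 60.5% suppressed.
- Group 6: 0.70 × 0.97^5 = 0.601 against 0.30 × 0.85^5 = 0.133, so 81.9% suppressed.

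| Stop per 6 months: suppressed / unsuppressed | A: start to 36 months | B: first to sixth group |
|---|---|---|
| 3% / 3% | 70.0% to 70.0% | 70.0% to 70.0% |
| 3% / 6% | 70.0% to 73.8% | 67.4% to 73.2% |
| 3% / 10% | 70.0% to 78.5% | 64.1% to 77.2% |
| 3% / 15% | 70.0% to 83.7% | 60.5% to 81.9% |
| 5% / 2% | 70.0% to 65.9% | 72.6% to 66.6% |

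Keeping every ever-treated patient (B) does not remove the artefact if they are sorted by time on drug.

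**Landmarks from initiation, all eligible starters.** In the same model with h_r = 0.03, the suppressed share is 70% at every landmark if viral load is known after stopping. If only on-drug suppression counts, it falls to 58.3% at 36 months. Neither shows a false rise.

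**The case against.** A reader might infer that the long-duration groups will consist mainly of responders and that response will falsely appear to improve. The documents do not support that. It requires non-responders to stop faster, and no stopping rate is given. The Background notes that second- and third-line options are limited, so failing patients may stay on these drugs. Start date and age exit also set duration and need not relate to response.

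A reader might also take time on drug to be the only grouping planned. Table 1 contradicts that with its axis counted from the last visit.

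Duration could further be read as time since initiation, in line with Table 2. With all starters kept, the problem then disappears. But Table 2 is an extraction schedule that sets no analysis denominator, and nothing in the text settles the reading.

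The plan has partial safeguards: it includes everyone ever treated and it describes retention. The first does not suffice (model B). The second is not linked to the viral load summaries.

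Finally, this is a descriptive chart review with no hypothesis test, and nowhere does it say that the groups will be read as durability. That limits the consequence, but the tables still need an axis and a denominator that can be interpreted.

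**Conclusion.** The concern holds in conditional form. Follow-up results are grouped by an undefined, potentially outcome-dependent duration, and the sections disagree on the time axis, so differences across groups cannot be taken as response over time.

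The size depends on assumed rates. With 70% suppressed and 3% of suppressed against 6% to 15% of unsuppressed patients stopping per 6 months, the apparent on-drug rise over 36 months is about 4 to 14 percentage points with no individual change. It is nil at equal rates and reverses if responders leave faster. The documents establish neither the direction nor the size of any actual distortion.

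**What to change.** In Methods and Timeline, Table 1 and Data Handling and Analysis, use one axis: time since DRV/ETR initiation, at 6, 12, 18, 24, 30 and 36 months.

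- **Denominator:** at each landmark, every patient who started at least that long before the data collection round.
- **Viral load:** the result nearest the landmark, within a stated window.
- **Separate categories:** on DRV/ETR and suppressed; on DRV/ETR and not suppressed; on DRV/ETR with no result; switched off DRV/ETR (with viral load if recorded); transitioned out of the donation program by age; died; lost or not in care.
- **Reporting:** the percentage suppressed among all eligible starters beside the on-drug percentage. Planned age transition must not count as failure, and the plan should say how those patients enter the denominator.
- **Caution:** state that on-drug percentages across time do not measure durability.

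**Cost.** Initiation date and current status must be listed explicitly in Table 1, which now lists duration on the drugs only under objective c. The promised duration and retention summaries already need both. Viral load results need their dates so that the window can be applied. The tables gain a few rows. The all-starter percentage will look less favourable than the on-drug one.
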